5.1.2 Leukapheresis Inclusion Criteria

A subject must meet all of the following criteria to be eligible for leukapheresis:

1. Written informed consent for leukapheresis is provided.
2. Weight ≥ 110 pounds.
3. Screening laboratory evaluations are within acceptable ranges at the site where the leukapheresis procedure will be performed.
4. Negative urine or serum pregnancy test at screening and on the day of the leukapheresis procedure for women of childbearing potential.
5. Adequate bilateral antecubital venous access.
6. No use of blood thinners, aspirin, or nonsteroidal anti-inflammatory drugs (NSAIDs) at least 5 days before the leukapheresis procedure.

5.1.3 Subject Exclusion Criteria

Subjects eligible to participate in this trial must not meet any of the following exclusion criteria:

1. History of prior confirmed (PCR or antigen test positive) COVID-19 less than 112 days prior to enrollment.
2. Positive for anti-nucleoprotein SARS-CoV-2 specific antibody by enzyme-linked immunosorbent assay (ELISA) and had the history of upper respiratory illness (URI) compatible with COVID-19 during the 112 days prior to enrollment (seropositivity without a history of URI during the 112 days prior to enrollment will be considered remotely infected persons eligible for enrollment).
3. Positive nasal swab polymerase chain reaction (PCR) at screening.
4. Body mass index (BMI) $> 30 \text{ kg/m}^2$ for Stage 1 participants and BMI $> 35 \text{ kg/m}^2$ for Stage 2 participants.
5. Presence of medical comorbidities that would place the subject at increased risk for severe COVID-19*.

**Chronic kidney disease, chronic lung disease (including moderate-to-severe asthma), chronic heart disease (heart failure, coronary artery disease or cardiomyopathies), cerebrovascular disease, diabetes mellitus, chronic liver disease, sickle cell disease.*

6. Increased risk of occupational exposure to SARS-CoV-2 (healthcare workers and emergency response personnel)*.

**Applies to Stage 1 participants only.*

7. Prior receipt of an approved/licensed or investigational SARS-CoV-2 vaccine (including under EUA)*, approved or investigational adenovirus-vectorized vaccines**, or any other approved or investigational vaccine likely to impact the interpretation of the trial data.

**Exclusion of prior receipt of EUA/licensed COVID-19 vaccines applies to Stage 1 participants only.*

***With the exception of prior receipt of EUA Johnson & Johnson/Janssen Ad 26 COVID-19 vaccine which is permitted for Groups 8 and 12.*

8. On current treatment or prevention agents with activity against SARS-CoV-2.

9. Current smoking or vaping or history of smoking or vaping in prior year*.

**Applies to Stage 1 participants only.*

10. Breastfeeding, pregnant, or planning to become pregnant during the course of the study.

11. Participation in another research study involving receipt of an investigational product in the 60 days preceding enrolment or planned use during the study period.

12. Receipt or planned receipt of any live, attenuated vaccine within 28 days before or after study vaccination.

13. Receipt or planned receipt of any subunit or killed vaccine within 14 days before or after vaccination.

14. Administration of immunoglobulins and/or any blood products within the three months preceding the planned administration of first study vaccination or at any time during the study.

15. Any confirmed or suspected immunosuppressive or immunodeficient state, including human immunodeficiency virus (HIV) infection, asplenia, recurrent, severe infections and chronic (more than 14 continuous days) immunosuppressant medication within the past 6 months (inhaled, ophthalmic, and topical steroids are allowed).

16. History of allergic disease or reactions likely to be exacerbated by any component of the vaccine, including urticaria, respiratory difficulty or abdominal pain (or any immediate

allergic reaction of any severity to polysorbate due to potential cross-reactive hypersensitivity with the polyethylene glycol component of the vaccine).

17. Any history of hereditary angioedema, acquired angioedema, or idiopathic angioedema.
18. Any history of anaphylaxis, including but not limited to reaction to vaccination.
19. Any history of severe allergic drug reaction.
20. History of cancer (except basal cell carcinoma of the skin and cervical carcinoma in situ).
21. History of serious ongoing, unstable psychiatric condition that in the opinion of the investigator would interfere with study participation.
22. Seizure in the past 3 years or treatment for seizure disorder in the past 3 years.
23. Bleeding disorder (e.g., factor deficiency, coagulopathy, or platelet disorder), or prior history of significant bleeding or bruising following IM injections or venipuncture or family history of bleeding disorder.
24. Recent (within the past 3 months) surgery, immobility, chronic infection, or head trauma that could increase the risks of thrombosis.
25. Suspected or known current alcohol abuse. Suspected or known drug abuse in the 5 years preceding enrollment.
26. Seropositive for HIV, hepatitis B surface antigen (HBsAg), or seropositive for hepatitis C virus (antibodies to HCV).
27. Have an acute illness* within 72 hours prior to study vaccination.

**An acute illness which is nearly resolved with only minor residual symptoms remaining is allowable if, in the opinion of the site PI or appropriate sub-investigator, the residual symptoms will not interfere with the ability to assess safety parameters as required by the protocol.*

28. History of venous or arterial thrombosis or any known thrombophilic condition including heparin-induced thrombocytopenia (HIT) or family history of thrombosis.
29. History of myocarditis or pericarditis.
30. History of Guillain-Barré Syndrome (GBS).
31. Receiving heparin treatment or on medications associated with increased risk of bleeding or thrombosis.

32. Any other condition that in the opinion of the investigator would pose a health risk to the participant if enrolled or could interfere with evaluation of the trial vaccine or interpretation of study results.

5.2 Delay of Study Vaccination, Withdrawal from the Study, Discontinuation of Study Product, or Study Termination

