[#]Participants in Groups 7, 8, 10, 11, and 12 will be enrolled in two subgroups: A (vaccinated, but no prior infection history) and B (vaccinated, and history or evidence of infection, but not within 4 months before enrollment), and the numbers of noninfected and infected subjects will not be pre-specified. For Groups 13-15, 7-10 subjects will be enrolled into each group that have been previously infected with SARS-CoV-2 at least 4 months earlier or not, and the numbers of noninfected and infected subjects to be enrolled will not be pre-specified.

**** After protocol version 9.0 was implemented, it was decided not to enroll subjects into Groups 7 and 8 because of competing priorities and predicted difficulties enrolling into these two groups.

Figure 1: Group Enrollment Flow Diagram*

Stage 1

Stage 2

(*Groups 1, 3A/B, and 4 were enrolled prior to protocol v5.0.)

(**Group 7 [≤ 60 yo] enrollment is dependent on Group 11 safety data per DSBM recommendations)

* After protocol version 9.0 was implemented, it was decided not to enroll subjects into Groups 7 and 8 because of competing priorities and predicted difficulties enrolling into these two groups.

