increasing to no more than 10 µg, as tolerated. Each dose escalation group will start with 3 sentinels followed for 72 hours before proceeding with the remaining volunteers in each group. At least 7 subjects enrolled in each dose escalation group will be evaluated through Day 8 post-vaccination before the protocol team decides on whether to further dose escalate. Subjects in Groups 3B and 4 who have received the prime vaccination will receive 3 µg of SAM-S or SAM-S-TCE, respectively as the second dose.

Due to the extensive roll-out of the EUA/licensed COVID-19 vaccines, no further enrollment will occur in Stage 1 (naïve subjects). Stage 2 groups focus on the use of SAM-S-TCE and ChAd-S-TCE as boosting vaccines in subjects who previously received a primary EUA/licensed COVID-19 vaccination series, with or without subsequent receipt of an approved COVID-19 booster vaccination. Because of the increasing prevalence of SARS-CoV-2 infection, and the need to understand how booster vaccines may impact pre-existing immunity, enrollment of subjects has also been extended to include both participants with previous but not acute evidence of infection (must be PCR negative at screening and have had no evidence of infection during the previous 4 months before screening), and those without prior infection history.

During the course of this trial the 10 µg dose of the same lot of the Gritstone SAM-S-TCE vaccine being used in DMID 20-0034 has been tested in 10 adults ≥ 60 years of age in a parallel trial in the UK. The subjects were previously vaccinated with the AstraZeneca ChAdOx1 COVID-19 vaccine and compared to similar subjects given boosts with the Moderna mRNA-1273 vaccine after ChAdOx1 primary vaccination. None of the elderly UK subjects boosted with 10 µg of SAM-S-TCE had any severe graded reactogenicity, and the boosting of neutralizing antibody responses was similar between those boosted with SAM-S-TCE and those boosted with the Moderna mRNA-1273. Concurrently, increasing evidence suggests that the mRNA vaccines are more reactogenic in younger compared with older people. Thus, in version 7.0 of this protocol dosing of SAM-S-TCE in older subjects will precede dosing with 10 µg of SAM-S-TCE in younger subjects.

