2.2.5 Study Population

The study population will include healthy adults aged 18 years and older, who are naïve or previously vaccinated with an EUA/licensed COVID-19 primary vaccination series with or without receipt of an approved/licensed COVID-19 booster vaccination. In addition, subjects that have experienced prior infection with SARS-CoV-2 or those not previously infected will be studied. However, subjects with recent (within the last 4 months of enrollment) or acute infection (PCR positive) will be excluded.

The full list of inclusion/exclusion criteria is provided in [Section 5.1](#).

The study will enroll subjects from at least 4 US-based IDCRC sites.

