6.1 Screening

Screening for this study will be completed through the participating institution's screening protocol or this study's informed consent. Testing will be done according to eligibility criteria and clinical assessment at screening. Screening evaluations for specific eligibility criteria must be completed within 30 days prior to enrollment for the given parameter but may be repeated as needed to confirm eligibility. If consent is obtained, the screening procedures indicated in the Schedule of Activities (see [Table 6](#), [Table 7](#), [Table 8](#), and [Table 9](#)) will be undertaken. To avoid unnecessary additional venipuncture, if the appropriate blood test results for screening are available for the same subject (e.g., recent doctor's visit), these results may be used for assessing eligibility provided the results date is within the 30 days preceding enrolment to this trial.

Abnormal clinical findings from the medical history, physical examination or blood tests at screening will be assessed. Abnormal blood tests following enrollment will be assessed according to the FDA guidance document "Toxicity Grading Scale for Healthy Adult and Adolescent Volunteers Enrolled in Preventive Vaccine Clinical Trials". If a test is deemed clinically significant it may be repeated to ensure it is not a single occurrence. If an abnormal finding is deemed to be clinically significant, the subject will be informed and referred for appropriate medical care with the permission of the subject. Decisions to exclude the subject from enrolling in the trial or to withdraw a subject from the trial will be at the discretion of the Investigator.

Any study subject who has not yet received the current year influenza vaccination may receive this, if available, during the screening period but not within 14 days before or after study treatment start.

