6.6.6 Visit 07, Day 57, Clinic Visit, 2nd Study Vaccination (Dose 2)

(Window: Day 57±3 days post 1st study vaccination)

In addition to the study procedures listed in [Section 6.6](#), the following study procedures will also be performed:

- Eligibility criteria will be reviewed with subjects prior to the second study vaccination to ensure continued eligibility.

- A urine or serum pregnancy test will be performed locally by the site within 24 hours prior to the second study vaccination for all women of childbearing potential. Results must be negative and known prior to the second study vaccination.
- Nasal swab will be collected for SARS-CoV-2 PCR prior to the second vaccination.
- Approximately 2 mL of venous blood will be collected for SARS-CoV-2 serology (N-specific).
- Approximately 14 mL of venous blood will be collected immediately prior to the second study vaccination for baseline clinical safety labs (WBC, HgB, PLT, ALT, AST, ALP, T Bili, CK, and Cr) to be performed by the local (clinical) laboratory. The results from these evaluations will not be available or reviewed prior to the second study vaccination.
- Approximately 72 mL of venous blood will be collected immediately prior to the second study vaccination for cellular immunology assays.
- Approximately 20 mL of venous blood will be collected immediately prior to the second study vaccination for antibody assays.
- Approximately 24 mL of venous blood will be collected for PBMC and plasma storage for secondary research.
- Approximately 2.5 mL of venous blood will be collected for identification of transcriptomal signatures associated with vaccine reactogenicity and immunogenicity.
- Approximately 4 mL of blood will be collected for cytokines.
- Subjects will then receive one- 0.25 or 0.5 mL dose of study vaccine (depending on treatment assignment) via a single IM injection into the deltoid muscle. If possible, administer study vaccine in the opposite arm used for the first study vaccination. The site of injection (right or left arm) and time of study vaccine administration to the subject will be recorded on the appropriate DCF. Subjects will be observed in the clinic for at least 45 minutes after the second study vaccination. The second study vaccination site will be examined, post-administration reactogenicity assessments will be performed, and any AEs/SAEs/AESIs including PIMMCs/MAAEs/NOCMCs will be recorded on the appropriate DCF prior to discharge from the clinic.

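### Infected subjects are described as at least 4 months post-infection, but recall and a screening sample up to 30 days old cannot establish this, so some recent infections can be classed as remote or as none

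*Protocol*

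**What the plan says.** **What the population is said to be.** Section 2.2.5 states that "subjects with recent (within the last 4 months of enrollment) or acute infection (PCR positive) will be excluded". The Table 1 footnote defines subgroup A as vaccinated with no prior infection history, and subgroup B as vaccinated with "history or evidence of infection, but not within 4 months before enrollment". It describes infected subjects in Groups 13-15 as infected at least 4 months earlier. Section 2.2 puts the condition in terms of evidence at screening: subjects "must be PCR negative at screening and have had no evidence of infection during the previous 4 months before screening".

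**What the criteria exclude (Section 5.1.3).**
- Exclusion 1: "History of prior confirmed (PCR or antigen test positive) COVID-19 less than 112 days prior to enrollment".
- Exclusion 2: N-seropositivity together with a COVID-compatible upper respiratory illness (URI) in the 112 days before enrollment. It adds that "seropositivity without a history of URI during the 112 days prior to enrollment will be considered remotely infected persons eligible for enrollment".
- Exclusion 3: "Positive nasal swab polymerase chain reaction (PCR) at screening".

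**When the tests are done.** Section 6.1 says "Screening evaluations for specific eligibility criteria must be completed within 30 days prior to enrollment"; repeating them is optional. Section 6.1.1 places the swab and N-serology at Visit 00 (Day -30 to -1). Section 6.2.1 and Tables 6-9 show neither on Day 1, although about 20 mL of blood for antibody assays is drawn then. Medical history comes from interview, and Section 11.1 says that this suffices.

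**A conflicting sentence.** Section 7.2.1 lists SARS-CoV-2 among the screening tests that must be negative for eligibility. Section 6.2.1 and exclusion 2 expressly admit seropositive, PCR-negative subjects.

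**The concern.** The descriptive text asserts a property of the subjects, namely time since infection. The criterion deems that property to hold; it does not establish it. N-seropositivity shows that an infection occurred, not when. For a subject with no positive test, the only dating information is whether a URI is remembered.

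Section 2.2 says infected subjects were admitted to learn how boosters may affect pre-existing immunity, so baseline infection status is the descriptor that readers of Groups 10-15 will use. An unrecognised infection close to dosing could add to the Day 15 and Day 29 rise credited to the vaccine. One some weeks earlier could raise the Day 1 level and shrink the fold-rise. Either also clouds the T cell epitope (TCE) readout, because Section 2.2.4 expects a single boost may only prime that response in subjects vaccinated against Spike alone.

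**Working it through.** There is no stated figure to reproduce for the claim itself. The check compares definitions and windows, then illustrates scale.

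**1. Two subjects traced through the rules.**
- *Subject X*: asymptomatic, never tested, infected 60 days before enrollment; at screening N-seropositive and PCR negative. Exclusion 1 does not apply (no positive test). Exclusion 2 does not apply (no URI). Exclusion 3 does not apply (PCR negative). X is eligible and deemed remotely infected: subgroup B in Groups 10-12, or an infected subject in Groups 13-15. Section 2.2.5 says such a person is excluded.
- *Subject Y*: PCR and N negative at screening on Day -25; asymptomatic, untested infection on Day -10. No Day 1 test can reveal it. Y is dosed and, on the screening results, falls in subgroup A.

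**2. Windows.** Up to 30 of the 112 look-back days can follow the only PCR and N-serology: 30/112 = 27%. Separately, 4 calendar months is 120 to 123 days, so the 112-day criterion is 8 to 11 days shorter than the 4 months in the text.

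**3. Chance that a group contains such a subject.** The protocol gives no infection rate, so let q be an assumed per-subject chance of misclassification by either route. The chance of at least one in n subjects is 1 − (1 − q)^n. The same formula reproduces the protocol's Table 4 (for example n = 10, rate 10%: 1 − 0.9^10 = 65.1%).

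| q (assumed) | n = 7 | n = 8 | n = 10 | n = 12 |
|---|---|---|---|---|
| 1% | 6.8% | 7.7% | 9.6% | 11.4% |
| 2% | 13.2% | 14.9% | 18.3% | 21.5% |
| 5% | 30.2% | 33.7% | 40.1% | 46.0% |

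**4. Effect of one such subject on a group GMT.** If that subject's titer is raised r-fold by infection (r assumed), the GMT is multiplied by r^(1/n).
- r = 10: 10^(1/7) = 1.39; 10^(1/8) = 1.33; 10^(1/10) = 1.26.
- r = 5 to 20 at n = 10: 5^(1/10) = 1.17 to 20^(1/10) = 1.35.
- The A/B split is not pre-specified, so a subgroup may be smaller: at an assumed n = 4, 10^(1/4) = 1.78.

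**5. Against the plan's own precision.** Upper-limit factors from Table 5 at SD 0.5 are 158.8/100 = 1.59 (n = 7), 151.9/100 = 1.52 (n = 8) and 143/100 = 1.43 (n = 10). At SD 1.0 they are 2.52, 2.31 and 2.04. The 10-fold shifts at those same three sizes lie inside these intervals. Averaged over whether an affected subject is present, the expected shift on the log scale is a factor of 10^q: 1.02, 1.05 and 1.12 for q = 1%, 2% and 5%.

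**The case against.** **The rule is disclosed.** Section 2.2 frames the condition as evidence at screening, the Table 1 footnote speaks of history or evidence, and exclusion 2 openly states a convention. No test in the protocol dates an asymptomatic infection, and Day 1 serology would not either. This is fair. It means the remedy is honest labelling, but it does not make the unqualified statement in Section 2.2.5 true.

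**There are safeguards.** Exclusion 1 removes any infection confirmed by PCR or antigen test within 112 days. Exclusion 2 removes seropositive subjects with a reported URI, and exclusion 3 a positive screening swab. Exclusion 27 bars acute illness within 72 hours of vaccination. The first two run to enrollment, and Day 1 repeats the eligibility review and interim history. The per-protocol population drops subjects found ineligible at baseline. These stand, and they confine the gap to infections neither tested nor noticed. A reader might infer that every N-seropositive subject is admitted as remote, or that recent infections do enter. The documents support only that some can, at an unknown rate.

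**The Dose 2 swab proves little.** In the two-dose groups, "Nasal swab will be collected for SARS-CoV-2 PCR prior to the second vaccination". A reader might infer that the protocol already regards a 30-day-old result as inadequate. That does not follow. By Dose 2 in Group 12 the screening swab is about 8 weeks old or more. The text also requires only that the swab be collected, whereas for the pregnancy test it requires a known negative result.

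**The consequence is small.** Immunogenicity is secondary and descriptive. Section 10.1 rules out hypothesis tests between groups, and the protocol sets no A-versus-B comparison. Groups 7 and 8 were not opened, so the A/B labels matter only for Groups 10-12. Groups 13-15 mix infected and uninfected subjects by design. All this is correct and limits the weight of the point.

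**Conclusion.** The point holds in this form. The protocol attributes to its infected subjects a time since infection that its criteria do not establish. An asymptomatic, untested infection within 112 days can be counted as remote, and one arising after screening can be counted as none. This follows from the text alone.

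The size is not known from the documents. The percentages rest on assumed rates of 1% to 5%, and the GMT factors on an assumed 5- to 20-fold effect in one subject. The direction is not fixed either, since an earlier infection can blunt the fold-rise. A reader might infer that the immunogenicity results are materially biased, or that the safety objective is compromised. Neither is supported: a 10-fold shift in one subject stays within the Table 5 intervals at n = 7, 8 and 10, and no hypothesis test depends on infection status. What is at stake is the correct description of a baseline characteristic in small groups. It is worth correcting because the correction is cheap.

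**What to change.** 1. Run N-serology on the Day 1 antibody serum already drawn, and use it with the screening result to classify baseline infection status for analysis. Table 12 allots 2 mL to the screening serology and 20 mL to Day 1 antibody serum, so no extra draw should be needed. For subjects already enrolled it can be done retrospectively if serum remains. It will not date an infection and can miss one too recent to have raised antibody.
2. Record the basis of prior-infection status in one eCRF field. Summarise documented infection at least 112 days earlier separately from N-seropositive with infection date unknown.
3. Reword Section 2.2.5 and the Table 1 footnote to match exclusion 2, and use one expression of the window (112 days or 4 months).
4. Reconcile Section 7.2.1, which requires negative SARS-CoV-2 screening tests, with exclusion 2 and Section 6.2.1, which admit seropositive subjects.

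The cost is a small assay charge, one data field and text changes. The downsides are very small descriptive subsets and a narrower claim about time since infection. Adding or moving a swab is not part of this fix. A reader might take it to be free, but a swab shortly before Day 1 would need an extra visit or a compressed screening period, and a swab on Day 1 an additional test.
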